7.3.2. Subject information

- Date of birth
- Gender
- Height/Weight
- Pregnancy: If 'yes', then record the week of pregnancy.
- Breast-feeding
- Diagnosis: Select one among 'Philadelphia (+) B-cell ALL', 'Philadelphia (-) B-cell ALL', or 'Unknown'.
- First Diagnosis date/First treatment date: Record approximate date if an actual date is unknown.

PFIZER CONFIDENTIAL

CT24-WI-GL02-RF01 6.0 Non-Interventional Study Protocol Template For Primary Data Collection Study 01-

Aug-2023

Page 13 of 37

- Current disease status: Select either 'refractory' or 'relapsed'. If 'relapsed', select one among 'first relapsed', 'second relapsed', or 'third or more relapsed'. Record the date of each onset. Record approximate date if an actual date is unknown.

7.3.3. Prior treatment history of B-cell precursor lymphoblastic leukemia

Prior to administrating BESPONSA®, if the subject received systemic therapy or hematopoietic cell transplant (HCT) to treat B-cell precursor lymphoblastic leukemia, record them. First, check among 'yes', 'no' or 'unknown'. If 'yes', record the followings.

7.3.3.1. Previous systemic therapy

- Regimen: Record the name of regimen.
- Purpose of treatment: Select one among 'induction', 'consolidation', 'maintenance', 'conditioning', or 'intensification'.
- Name of treatment drug: Record generic name.
- Duration of administration: Record the start date and stop date. Record approximate date if an actual date is unknown.
- Best response to therapy: First, check among 'conducted', 'not conducted' or 'unknown'. If 'conducted', record the date of evaluation and select one among 'complete response (CR)', 'CR with incomplete blood count recovery (CRi)', 'refractory disease', or 'progressive disease'. Response Criteria is defined according to *'NCCN Guideline Version 2.2016 Acute Lymphoblastic Leukemia'*⁹. Refer to Appendix 1 for detailed Response Criteria.

7.3.3.2. Previous Hematopoietic cell transplant

- Date of HCT: Record approximate date if an actual date is unknown.
- Best response to therapy: First, check among 'conducted', 'not conducted' or 'unknown'. If 'conducted', record the date of evaluation and select one among 'CR', 'CRi', 'refractory disease', or 'progressive disease'.

7.3.4. Medical History

Select among 'yes' or 'no' for medical history of followings. Past or present disease will be determined based on the first BESPONSA® administration date. Record adequate full name of the disease down as the Medical Terminology Dictionary indicates (written by Korean Medical Society).

7.3.4.1. Hepatic disorder / Renal disorder

If 'yes', record the name of the disease, severity and status.

Every subject must be evaluated whether he/she has ever had venoocclusive liver disease/sinusoidal obstruction syndrome (VOD/SOS). If he/she has, check 'yes' and select severity. Check 'no' if he/she had never had.

7.3.4.2. Allergic history

If 'yes', record the allergen and status.

7.3.4.3. Other diseases / symptoms

If 'yes', record the name of the disease and status.

7.3.5. Concomitant Medication

Record the concomitant medication including the transfusion while BESPONSA® is being administrated. First select either 'yes' or 'no' then record in more details if selected 'yes'.

- Name of medication: Record generic name.
- Treatment start date
- Treatment stop date: If the treatment is not terminated until the timing of CRF completion, leave it blank.
- Ongoing: If the treatment is not terminated until the timing of CRF completion, check 'ongoing'.
- Purpose of treatment: Select one among 'treatment for B-cell ALL', 'treatment for other diseases', 'treatment for an adverse event', 'prevention of drug side effect', or 'other'. If 'other', record the specific reason.

7.3.6. Administration status and response evaluation for each cycle of BESPONSA®

Record the following with regard to administrative status and response evaluation for each cycle. Record administrative status of all cycle until the last administration dose. Refer to LPD for posology and method of administration.

- Administration date

- Body surface area
- Administration dose
- Pre-medication: If 'conducted', record the detailed information in '4.Concomitant medication' clause in CRF.
- Response evaluation after each cycle: Record the evaluation date and response. Select one among 'CR', 'CRI', 'refractory disease', 'progressive disease', or 'relapsed disease'. Response Criteria is defined according to *NCCN Guideline Version 2.2016 Acute Lymphoblastic Leukemia*⁹. Refer to Appendix 1 for detailed Response Criteria. If response evaluation is not done, check 'undone' and leave the evaluation date blank.

7.3.7. Final effectiveness evaluation

Record the final effectiveness after all cycle of BESPONSA® is finished.

Check 'conducted' if final effectiveness is evaluated then record the date of evaluation. Check 'not conducted' if final effectiveness is not evaluated then select one reason why it is not conducted among 'death', 'follow up loss', or 'other'. If 'other', record the specific reason.

- Response criteria: Select one among 'CR', 'CRI', 'refractory disease', 'progressive disease', or 'Relapsed disease'.
- Plan for HCT: Check 'yes' if HCT is on plan or on ongoing for a subject.

7.3.8. Safety Evaluation

Safety will be assessed based on adverse events reported for all patients who received at least one dose of BESPONSA® and completed safety follow-up. Every observed and reported adverse event, regardless of the causal relationship with the study drug, must be recorded on an safety evaluation section in CRF

7.3.8.1. Definition of adverse events

An adverse event (AE) is any untoward medical occurrence in a patient administered a medicinal product. The event need not necessarily have a causal relationship with the product treatment or usage. Examples of adverse events include but are not limited to:

- Abnormal test findings (see below for circumstances in which an abnormal test finding constitutes an AE);
- Clinically significant symptoms and signs;

PFIZER CONFIDENTIAL

- Changes in physical examination findings;
- Hypersensitivity;
- Progression/worsening of underlying disease;
- Lack of efficacy;
- Drug abuse;
- Drug dependency.

Additionally, for medicinal products, they may include the signs or symptoms resulting from:

- Drug overdose;
- Drug withdrawal;
- Drug misuse;
- Off-label use;
- Drug interactions;
- Extravasation;
- Exposure during pregnancy;
- Exposure during breast feeding;
- Medication error;
- Occupational exposure.

Abnormal test findings

The criteria for determining whether an abnormal objective test finding should be reported as an adverse event are as follows:

- Test result is associated with accompanying symptoms, and/or
- Test result requires additional diagnostic testing or medical/surgical intervention, and/or
- Test result leads to a change in study dosing or discontinuation from the study, significant additional concomitant drug treatment, or other therapy, and/or

PFIZER CONFIDENTIAL

- Test result is considered to be an adverse event by the investigator or sponsor.

Merely repeating an abnormal test, in the absence of any of the above conditions, does not constitute an adverse event. Any abnormal test result that is determined to be an error does not require reporting as an adverse event.

7.3.8.2. Definition of serious adverse events (SAEs)

A serious adverse event is any untoward medical occurrence in a patient administered a medicinal or nutritional product (including pediatric formulas) at any dose that:

- Results in death;
- Is life-threatening;
- Requires inpatient hospitalization or prolongation of hospitalization (see below for circumstances that do not constitute adverse events);
- Results in persistent or significant disability/incapacity (substantial disruption of the ability to conduct normal life functions);
- Results in congenital anomaly/birth defect;

Progression of the malignancy under study (including signs and symptoms of progression) should not be reported as a serious adverse event unless the outcome is fatal within the safety reporting period. Hospitalization due to signs and symptoms of disease progression should not be reported as a serious adverse event. If the malignancy has a fatal outcome during the study or within the safety reporting period, then the event leading to death must be recorded as an adverse event and as a serious adverse event with severity Grade 5.

Medical and scientific judgment is exercised in determining whether an event is an important medical event. An important medical event may not be immediately life-threatening and/or result in death or hospitalization. However, if it is determined that the event may jeopardize the patient or may require intervention to prevent one of the other outcomes listed in the definition above, the important medical event should be reported as serious.

Examples of such events are intensive treatment in an emergency room or at home for allergic bronchospasm; blood dyscrasias or convulsions that do not result in hospitalization; or development of drug dependency or drug abuse.

Additionally, any suspected transmission via a Pfizer product of an infectious agent, pathogenic or non-pathogenic, is considered serious. The event may be suspected from clinical symptoms or laboratory findings indicating an infection in a patient exposed to a Pfizer product. The terms “suspected transmission” and “transmission” are considered synonymous. These cases are considered unexpected and handled as serious expedited cases

by PV personnel. Such cases are also considered for reporting as product defects, if appropriate.

Hospitalization

Hospitalization is defined as any initial admission (even if less than 24 hours) to a hospital or equivalent healthcare facility or any prolongation to an existing admission. Admission also includes transfer within the hospital to an acute/intensive care unit (e.g., from the psychiatric wing to a medical floor, medical floor to a coronary care unit, neurological floor to a tuberculosis unit). An emergency room visit does not necessarily constitute a hospitalization; however, an event leading to an emergency room visit should be assessed for medical importance.

Hospitalization in the absence of a medical AE is not in itself an AE and is not reportable. For example, the following reports of hospitalization without a medical AE are not to be reported:

- Social admission (e.g., patient has no place to sleep)
- Administrative admission (e.g., for yearly exam)
- Optional admission not associated with a precipitating medical AE (e.g., for elective cosmetic surgery)
- Hospitalization for observation without a medical AE
- Admission for treatment of a pre-existing condition not associated with the development of a new AE or with a worsening of the pre-existing condition (e.g., for work-up of persistent pre-treatment lab abnormality)

7.3.8.3. Adverse events data collection

The investigator collects data on safety events as specified in Section 7 including all adverse events that occur during the observation period regardless of causal relationship to BESPONSA®. The information on adverse events should include the specific conditions or events, duration of the events (start date and stop date), severity, actions taken, seriousness (serious or non-serious), outcome and causal relationship to BESPONSA®.

Check either 'yes' or 'no' in adverse event occurrence section. If 'yes', record in detail.

- Adverse events: Record the name of adverse event. If possible, specify diagnosis, not individual symptoms. Record the name according to '*National Cancer Institute (NCI) Common Terminology Criteria for Adverse Events (CTCAE) Version 4.0*¹⁰'.

- Date of onset: Record the date of onset. Record approximate date if an actual date is unknown.
- Severity: Severity evaluation of AE must be done according to grades of 'NCI CTCAE Version 4.0¹⁰'. If the severity of an AE changed, the AE must be entered separately. Record stop date of previous severity and onset date of new severity – along with completion of all other items.
- Action: Check relevant action of BESPONSA® dosage. Select one among 'withdrawn (temporarily or permanently, or delayed)', 'dose reduced', 'dose increased', 'does not changed', 'unknown', or 'not applicable'.
- Seriousness: Check either 'yes' or 'no'. If 'yes', record the appropriate number for the category of seriousness.

A serious adverse event is any untoward medical occurrence at any dose that:

- ① Results in death;
- ② Is life-threatening;
- ③ Requires inpatient hospitalization or prolongation of hospitalization;
- ④ Results in persistent or significant disability/incapacity (substantial disruption of the ability to conduct normal life functions);
- ⑤ Results in congenital anomaly/birth defect.
- ⑥ Is important medical event (if it is determined that the event may jeopardize the subject or may require intervention to prevent one of the other outcomes listed in the definition above)

Check the following at the end of the study or after the resolution of AE.

- Outcome: Check one among 'Recovered', 'Recovered with sequelae', 'Recovering', 'Not recovered' or 'Unknown' as a reply to a question; 'Is the AE still present?'. If the status has resolved, record the date of resolution. Record approximate date if an actual date is unknown.
- Causality of adverse event to the study drug: The causal relationship of adverse event to the study drug must be allocated by the physician according to the following criteria.

① Certain

- It follows a reasonable time sequence from administration of the drug (before and after the study medication).
- It could not be explained by other drugs, chemical substance or accompanying diseases.
- It has clinically reasonable reaction on cessation of the drug.
- It has pharmacological or phenomenological reaction to re-administration of the drug, where necessary.

② Probable/likely

- It follows a reasonable time sequence from administration of the drug (before and after the study medication).
- It could not be explained by other drugs, chemical substance or accompanying diseases.
- It has clinically reasonable reaction on cessation of the drug. (No information on re-administration)

③ Possible

- It follows a reasonable time sequence from administration of the drug.
- It could also be explained by other drugs, chemical substance or accompanying diseases.
- It lacks information or has unclear information on discontinuation of the drug.

④ Unlikely

- It is not likely to have a reasonable causal relationship from administration of the drug. Rather, it seems to be temporary.
- It could also be reasonably explained by other drugs, chemical substances or latent diseases.

* Other causality of adverse event: If the adverse event is not related to the study drug, physicians should indicate the most appropriate cause from the followings and record in detail.

(1) Disease under the study

(2) Other disease (please specify)

PFIZER CONFIDENTIAL

(3) Concomitant treatment drug or non-drug (please specify)

(4) Others (please specify)

⑤ Conditional/unclassified

[figure not shown]
- It needs more data to make an appropriate assessment or its additional data are being reviewed.

⑥ Unaccessible/unclassifiable

- Lack of sufficient information or conflicting information hampers accurate causality assessment or supplementation or confirmation.

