7.2.3. Duration of the study

According to MFDS re-examination regulation, the re-examination report based on collected data of 6 years must be submitted to MFDS within 3 months after the end of specified re-examination period (from the product approval date to 6 years afterwards).

The data collection period of this study is until the required subject number (100 patients) is collected. The observation period for each subject is from initiating administration of first dose of BESPONSA® to the end of the observation period of the study, which must include at least 28 calendar days following the last administration of a BESPONSA®. In case of patient that Hematopoietic Stem Cell Transplant (HSCT) after administrated BESPONSA®, follow-up until 180 days after transplantation. All the data collected during the observation period should be recorded in the case report form (CRF). In case of an adverse event/safety event recognized after the observation period ends, it should be recorded in the CRF as specified in Section 7.

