7.7.3. Interim Analysis

As required by MFDS regulations, the periodic report should be submitted to MFDS every 6 months for the first two years and then annual report should be submitted to MFDS for the third, fourth and fifth year. The final report should be submitted in the sixth year. Interim analysis will be performed in time for the report submission.

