3. INTERIM ANALYSES

As required by MFDS regulations, the periodic interim report along with RMP report would be submitted to MFDS every 6 months for the first two years and then annual report would be submitted to MFDS for the third, fourth and fifth year. The final report would be submitted in the sixth year refer to RMP milestone.

All data collected will be integrated and reported in the sixth re-examination report.

Periodic report	Surveillance period	MFDS Submission Timeline
1-1st	2019-01-03 ~ 2019-07-02	2019-09-02
1-2nd	2019-07-03 ~ 2020-01-02	2020-03-02
2-1st	2020-01-03 ~ 2020-07-02	2020-09-02
2-2nd	2020-07-03 ~ 2021-01-02	2021-03-02
3rd	2021-01-03 ~ 2022-01-02	2022-03-02
4th	2022-01-03 ~ 2023-01-02	2023-03-02
5th	2023-01-03 ~ 2024-01-02	2024-03-02
Re-examination report	2024-01-03 ~ 2025-01-02	2025-04-02

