7. HANDLING OF MISSING VALUES

There are no plans for imputation of missing values for variables; all missing values will be excluded from corresponding analyses. The impact of missing data will be evaluated as appropriate.

However, if the causality of the study drug on adverse event is missing, it will be considered 'related' and classified as adverse drug reaction(ADR).

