8.2.2 Safety Analyses

The safety analyses will be performed for Safety analysis set. And all adverse events (AE) will be standardized by MedDRA version 22.1 (or the latest version at the time of analysis).

Adverse events which causality is missing or not 'unlikely' will be considered as adverse drug reaction (ADR).

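### Causality may be left blank until an AE resolves or the study ends, but the SAP counts blank causality as related, so AEs still open at a periodic cut-off can be reported as ADRs whatever their cause

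*Protocol*

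**What the plan says.** - **When causality is entered.** Protocol 7.3.8.3 lists the AE name, onset, severity, action and seriousness, and then instructs: "Check the following at the end of the study or after the resolution of AE". Two bullets follow, outcome and causality. On causality it says "The causal relationship of adverse event to the study drug must be allocated by the physician according to the following criteria", with no earlier time point.
- **What happens to a blank.** SAP 7 makes one exception to its rule against imputation: "if the causality of the study drug on adverse event is missing, it will be considered 'related' and classified as adverse drug reaction(ADR". SAP 8.2.2 builds this into the ADR definition: "Adverse events which causality is missing or not 'unlikely' will be considered as adverse drug reaction (ADR".
- **When the data are analysed.** Protocol 7.7.3 says "Interim analysis will be performed in time for the report submission". SAP 3 lists seven periodic reports before the re-examination report. The first covers "2019-01-03 ~ 2019-07-02".
- **How long patients are observed.** Protocol 7.2.3 sets an observation period "which must include at least 28 calendar days following the last administration of a BESPONSA" and, for transplanted patients, "follow-up until 180 days after transplantation".
- **The other causality duty.** Protocol 9.3 requires the investigator to assess and record causality for every AE, without saying when. For AEs judged related, it requires follow-up until they resolve or stabilise.

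**The concern.** Treating missing causality as related is a reasonable conservative rule for blanks left by oversight. Here it also catches blanks that the protocol permits. If an AE is open at a cut-off, a compliant site may not yet have entered causality, and the SAP does not distinguish an entry not yet due from one that is missing. The periodic ADR counts would then partly reflect how many AEs were open on the cut-off date. They could fall in a later report as entries are completed, which could be misread as a change in the safety profile. Serious and unexpected reactions are the first two stated objectives, and these tables go to the regulator.

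The protocol also disagrees with itself. Under 9.3, whether an AE must be followed to resolution depends on its being judged related, whereas 7.3.8.3 lets that judgement wait until the AE has resolved.

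**Working it through.** The plan states no figure on this point, so there is none to reproduce. The check has a textual part and two illustrative calculations.

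**1. Does any text prevent the blanks or keep them out of the tables?**
- Protocol 9.3 requires causality but sets no time, so it does not override 7.3.8.3.
- Protocol 7.3.8 bases safety on patients who completed safety follow-up, which would remove most open cases. SAP 5.1 does not carry this over. It requires one safety evaluation, and its follow-up-failure exclusion concerns AE status that was never evaluated, not AEs still open.
- The end of the study is not defined as the patient's or the whole study's. If it is the patient's, blanks can last only while that patient is under observation. If it is the whole study's, an AE unresolved when a patient dies or is lost could stay blank through several periodic reports. Either trigger should have been reached before the final report, which under SAP 3 integrates all data.

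So the route from an open AE to an ADR count is available in periodic reports and should largely close by the final one.

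**2. How often is a patient's observation window still open at a cut-off?**
Inputs: the surveillance periods in SAP 3 last 181, 184, 182 and 184 days, then 365 days each for the third to fifth years. The windows in Protocol 7.2.3 are 28 and 180 days. Assumption: windows of length L start uniformly over a period of length T. Formula: min(1, L/T).

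| Window | Six-month periods | Yearly periods |
|---|---|---|
| 28 days after last dose | 28/184 to 28/181 = 15.2% to 15.5% | 28/365 = 7.7% |
| 180 days after transplant | 180/184 to 180/181 = 97.8% to 99.4% | 180/365 = 49.3% |

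These are chances that observation is still running, not shares of AEs with blank causality. They show only that patients under observation at a cut-off are to be expected.

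**3. What would blanks do to the ADR share?**
Let p be the share of AEs that would be ADRs once assessed, meaning any category except unlikely. Let m be the share with causality blank at the cut-off because the AE is open. Assume that being blank is unrelated to the eventual assessment.

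Reported share = p(1 − m) + m = p + m(1 − p), so the inflation is m(1 − p).

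The documents give neither p nor m. For assumed ranges, the reported share (with inflation in percentage points) is:

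| p | m = 5% | m = 10% | m = 20% |
|---|---|---|---|
| 30% | 33.5% (+3.5) | 37% (+7) | 44% (+14) |
| 50% | 52.5% (+2.5) | 55% (+5) | 60% (+10) |
| 70% | 71.5% (+1.5) | 73% (+3) | 76% (+6) |

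The inflation runs from 1.5 to 14 points. It shrinks as p rises, and p may be high because five of the six causality categories count as ADRs.

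**4. After the change.** If causality is recorded at AE entry, m due to timing is 0 and the reported share equals p. AEs entered as Conditional/unclassified would still count as ADRs under SAP 8.2.2, and p already includes them.

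**The case against.** The strongest reply is that the protocol does not forbid earlier entry, and other text points towards it. The follow-up duty in 9.3 presupposes an early judgement. A finding that the drug did not cause an event of undetermined etiology is to be documented on both the CRF and the safety form. A change in severity requires a new entry with all other items completed, possibly while the AE continues. Whether the timing instruction governs causality as well as outcome also depends on the list layout. This stands in part: many sites may enter causality early. It does not remove the problem, because 7.3.8.3 gives no other time point and a site that waits is following it.

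The plan also has safeguards. SAP 8.2.2.1 tabulates events with missing causality, and Protocol 7.6 sends missing data to query. Readers of a periodic report can therefore see how many AEs lack causality. But the ADR, serious ADR and unexpected ADR tables still merge those blanks with assessed events.

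A reader might go further and infer three things that the documents do not support:
- **That the final report stays inflated for patients who die or are lost with an open AE.** The end of the study is an alternative trigger, and the outcome options include unresolved states, so these items are meant to be completed for such AEs too.
- **That serious ADRs are hit hardest.** The documents give no rates of non-resolution by seriousness, and serious events are reported within 24 hours on a separate form. Nothing says, however, that a causality view given there fills the CRF field.
- **That waiting for the outcome is itself a bias.** The two highest causality categories use the reaction after stopping the drug, so later information is part of the scale.

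**Conclusion.** The point holds in a limited form and is minor. As written, the protocol lets causality stay blank while an AE is open, and the SAP then counts that AE as an ADR. Periodic ADR counts can be inflated as a result. Separately, the timing in 7.3.8.3 and the follow-up duty in 9.3 need to be reconciled.

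The size cannot be determined from the documents. The range of 1.5 to 14 percentage points rests wholly on the assumed p and m. It would be near zero if sites enter causality early, or if periodic tables are limited to patients who have completed follow-up.

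The practical reach is also limited. The SAP follows protocol Amendment 4 of 7 November 2023. By the planned dates, six of the seven periodic submissions (September 2019 to March 2023) were already due, leaving only that of 2 March 2024. The study is descriptive, with no formal hypothesis. It would be wrong to conclude that the missing-as-related rule is an error. The difficulty is its combination with deferred entry.

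**What to change.** - **Protocol 7.3.8.3:** require an initial causality entry when the AE is first recorded, with an update at resolution or at the end of that patient's observation. State that the end of the study means the end of that patient's observation. This also settles the conflict with 9.3.
- **SAP 7 and 8.2.2:** keep the missing-as-related rule for entries still blank after query.
- **Periodic ADR tables:** show ADRs due solely to missing causality on a separate line, kept within the total. Removing them would treat a blank less conservatively than an AE expressly entered as Conditional/unclassified, which the SAP counts as an ADR.

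The cost is a short change to the CRF instruction, a sentence in the SAP and one extra table line. The downside is that sites may need to update a causality entry once.
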